Study protocol:
Impact of Repeated Antioxidant
Supplementation of Embryo Culture Media on
Blastocyst Utilization and Expansion Rate Under
Two Different O₂
Concentrations

October 31st, 2021

Title: The Role of Antioxidants in Mitigating Reactive Oxygen Species and Oxidative Stress in Assisted Reproduction Techniques: A Comparative Study

Introduction:

During assisted reproduction techniques (ARTs), monitoring the laboratory environment is essential for adequate embryo development and any deviation from optimal conditions could increase reactive oxygen species (ROS) (Kaskar, 2021). Excessive ROS is detrimental to early embryo development (Kaskar, 2021). Reactive oxygen species constitute highly reactive chemicals associated with oxidative stress (OS) and subsequent cellular damage to gametes and embryos (Lane & Lyons, 2000; Swain, 2010). Oxidative stress is observed when the accumulation of ROS molecules exceeds the capacity of antioxidants (AOXs) defense mechanisms to neutralize them, subsequently promoting lipid, protein, as well as DNA damage (Lane & Lyons, 2000; Swain, 2010).

In the past, embryo culture was performed in atmospheric O₂ concentrations of about 20% (Nastri et al., 2016). However, an O₂ concentration of 5% was found superior in terms of enhancing clinical pregnancy rate, live births, as well as implantation rate (Kaskar, 2021). Several exogenous factors affecting embryo development during in vitro culture, namely the type of infertility, as well as advanced maternal and paternal age, have been correlated with high levels of ROS production in gametes and embryos, which in turn result in decreased fertilization, implantation, and live birth rates, and increasing aneuploidy rates (Lane & Lyons, 2000; Edwards et al., 1998; Hong et al., 2014; Chui et al., 2008)

Therefore, it is conceivable that even minimal handling of gamete and embryos could induce OS. This assumption highlights the demand for strategies aiming to reduce the detrimental effects of OS. Implementation of AOX supplementation could help protect against OS damage attributed to alterations in laboratory conditions in the IVF setup. Antioxidants act as a counterpart of ROS, inhibiting their overproduction or neutralizing them when provided in sufficient concentrations (Agarwal et al., 2005; Carocho & Ferreira, 2013). The role of AOXs in enhancing the embryo's potential to successfully reach the blastocyst stage has been demonstrated (Guerin, 2001; Budani & Tiboni, 2020). The blastocyst quality of the expansion grade has been analyzed by the measurement of the blastocoel and has been associated with increased ongoing pregnancy rates (David Gardner et al., 1999)

Considering the pivotal role of AOXs *in vivo*, their implementation in embryo cultures *in vitro* is thought to help mimic the human reproductive tract's natural conditions. Previous studies have investigated the role of non-enzymatic AOX molecules namely vitamin C, vitamin E, selenium, zinc, taurine, hypotaurine, glutathione, and carotene on embryo culture (Agarwal et al., 2005; Carocho & Ferreira, 2013).

Previously, our group determined the oxidation-reduction potential (ORP) values of follicular fluid in oocyte donors and established them as the "physiological" desirable ORP in embryo culture media to maintain a redox state during the entire embryo culture similar to what is observed *in vivo* (Truong, T., & Gardner, D.K., 2017)

However, the current literature is lacking studies to develop a physiological *in vitro* AOXs system that can effectively mitigate the OS phenomenon.

The present study aims to explore whether repeated supplementation of the embryo culture medium with AOXs every 12 hours to culture embryos in ORP physiological levels, could improve the cumulative rates of usable and expanded blastocysts of human embryos from infertile patients as assessed at two different O₂ concentrations (5% and 20% O₂) on days 5 and 6.

Research Design:

Study type: Interventional

Study Model: Parallel Assignment

Participants: 293 Infertile women aged 18 to 37 years at the time of oocyte collection, with tubal factor, polycystic ovary syndrome, uterine factor, or unexplained infertility.

Allocation

Zygotes will be randomly assigned to one of four groups.

- Group 1A: Antioxidants will be administered every 12 hours at 5% O₂ tension.
- Group 1B: Antioxidants will be administered every 12 hours at 20% O₂ tension.
- Group 2A: Antioxidants will be administered once at the beginning of embryo culture at 5% O₂ tension.
- Group 2B: Antioxidants will be administered once at the beginning of embryo culture at 5% O₂ tension.

Methods:

Study Location and Duration:

The study will be conducted at the Center for Technological Innovation and Reproductive Medicine (CITMER), Mexico City, Mexico, from October 2021 to May 2022.

Participants:

Eligible participants will include infertile women with tubal factor, polycystic ovary syndrome, uterine factor, and unexplained infertility, who have had fertilization of more than 2 oocytes by conventional in vitro fertilization (cIVF) and intracytoplasmic sperm injection (ICSI).

Exclusion criteria will involve low ovarian response patients (fewer than 6 oocytes obtained after oocyte retrieval) and patients older than 37 years.

Sample Size and Group Allocation:

A total of 3603 zygotes obtained from 293 patients will be included in the study.

The zygotes will be divided into four groups based on the following conditions:

Group 1A: Antioxidants will be administered every 12 hours at 20% O₂ tension (793 zygotes).

Group 1B: Antioxidants will be administered only at the beginning of embryo culture at 20% O₂ tension (1286 zygotes).

Group 2A: Antioxidants will be administered every 12 hours at 5% O₂ tension (695 zygotes).

Group 2B: Antioxidants will be administered only at the beginning of embryo culture at (829 zygotes).

The procedures followed for IVF/ICSI involved the following steps:**Ovarian stimulation:**

Different ovarian stimulation protocols were used, including the gonadotropin-releasing hormone (GnRH) antagonist protocol with Cetrotide®, in combination with rFSH and rLH in Pergoveris®.

GnRH antagonist protocols were also used with follitropin alfa in Gonal-F® or with human menopausal gonadotropin in Merapur®

Gamete Retrieval:

Oocyte retrieval will be performed 36 hours after the administration of choriogonadotropin alfa (Ovidrell®, Merck Serono, Bari, Italy). Cumulus-oocyte complexes (COCs) will be transferred into dishes containing HTF HEPES® (InVitroCare®) supplemented with 10% human serum albumin (HSA) (InVitroCare®) and antioxidants (EmbryORP®). COCs will then be washed and placed in culture media (global® total®, Life global® Group) with stock antioxidants (EmbryORP®) until insemination.

Fertilization:

For intracytoplasmic sperm injection (ICSI) cases, mature oocytes (metaphase II) will be denuded using Hyaluronidase (10%) (InVitroCare®) approximately 40 hours after HCG administration. Only mature oocytes will be selected and injected. For conventional IVF insemination, oocytes will be co-incubated individually with capacitated sperm in embryo culture media for 17 to 20 hours.

Embryo Culture:

After the fertilization check, zygotes will be cultured under specific conditions in an incubator. The incubator settings will be either 37°C, 8% CO₂, 20% O₂, and 95% relative humidity (RH) or 37°C, 8% CO₂, 5% O₂, and 25% RH. Only 2 pronuclei (PN) zygotes will be considered for the study.

Antioxidant Supplementation:

The antioxidant supplementation protocol will involve the use of EmbryORP®, a novel antioxidant consisting of a mixture of four different compounds: reduced L- cysteine, L- glutathione, L- ascorbic acid, and L- carnitine hydrochloride (0.0124 M for carnitine, 0.0165 M for cysteine, 0.0065 M for glutathione, and 0.0227 M for ascorbic acid). Groups 1A and 2A, 6.5 µL of EmbryORP® antioxidants will be added at the beginning of the culture (in the zygote stage), followed by the addition of 3.5 µL of stock antioxidant media (EmbryORP®) every 12 hours. For groups 1B and 2B, 6.5 µL of EmbryORP® antioxidants will be added only at the beginning of the culture control of O₂ Tensions:

During embryo culture, two different O₂ tensions will be maintained. The first setting will be 20% O₂, and the second setting will be 5% O₂. These O₂ tensions will be controlled using the incubator, which will provide the desired atmospheric conditions.

Data Collection:**Variables to be Measured:**

The blastocyst expansion rate will be assessed by calculating the proportion of blastocysts that reach the expanded stage. Embryo evaluation will be performed based on the Gardner and Schoolcraft criteria from 1999, and the results will be documented in standardized databases.

Timeline and Frequency of Assessments:

Data collection will be performed at specific time points, specifically on day 5 and day 6 of the study.

Outcome Measures:

- Usable blastocysts on day 5.
- Expanded blastocysts on day 5.
- Usable blastocysts on day 6.
- Expanded blastocysts on day 6.
- Cumulative usable blastocysts.
- Cumulative expanded blastocysts.

Ethical Considerations:

The study was conducted in accordance with the Declaration of Helsinki and approved by the Institutional Ethics Committee of CITMER CE-20-102.

Data analysis

The statistical analysis of the data will be performed using the R statistical software by the R Core Team.

Statistical Methods:

For statistical analysis, the data collected consisted of the continuous variable of age, which was expressed as the mean \pm standard deviation in each study group. In addition, the frequency and percentage of usable and expanded blastocysts were recorded as categorical variables.

Comparisons between usable and expanded blastocysts from each treatment were performed by calculating the odds ratio and chi-square test. A significance level of $p < 0.05$ was established to determine the existence of statistically significant differences between groups.

References.

1. Khalied Kaskar, C. Optimizing embryo culture conditions and spent culture media analysis as predictors of embryo quality and pregnancy; PhD Thesis, University of the West Cape, Cape Town, South Africa, February 2021.
2. Swain, J.E. Optimizing the culture Environment in the IVF Laboratory: Impact of PH and Buffer Capacity on Gamete and Embryo Quality. *Reprod Biomed Online* **2010**, *21*, 6–16.
4. Nastri, C.O.; Nóbrega, B.N.; Teixeira, D.M.; Amorim, J.; Diniz, L.M.M.; Barbosa, M.W.P.; Giorgi, V.S.I.; Pileggi, V.N.; Martins, W.P. Low versus Atmospheric Oxygen Tension for Embryo Culture in

Assisted Reproduction: A Systematic Review and Meta-Analysis. *Fertil Steril* **2016**, *106*, 95-104.e17, doi:10.1016/j.fertnstert.2016.02.037.

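### The protocol defines the four groups twice with conflicting conditions, and the list under random assignment repeats one condition and has no once-only group at 20% O₂

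*Protocol*

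**What the plan says.** The aim, at the end of the protocol's Introduction, is to test whether supplementation every 12 hours improves blastocyst outcomes "as assessed at two different O₂ concentrations (5% and 20% O₂) on days 5 and 6". The Allocation section states "Zygotes will be randomly assigned to one of four groups" and then lists the groups:

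- The first entry is repeated supplementation at the lower tension: "Group 1A: Antioxidants will be administered every 12 hours at 5% O₂ tension".
- The second keeps that frequency and changes the oxygen: "Group 1B: Antioxidants will be administered every 12 hours at 20% O₂ tension".
- The third moves to a single addition: "Group 2A: Antioxidants will be administered once at the beginning of embryo culture at 5% O₂ tension".
- The fourth, 2B, has the same wording as 2A: once, at 5% O₂.

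The Sample Size and Group Allocation section lists them again, with counts:

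- The first entry is now at the higher tension: "Group 1A: Antioxidants will be administered every 12 hours at 20% O₂ tension (793 zygotes".
- The second is now a single addition: "Group 1B: Antioxidants will be administered only at the beginning of embryo culture at 20% O₂ tension (1286 zygotes".
- The third is now repeated supplementation: "Group 2A: Antioxidants will be administered every 12 hours at 5% O₂ tension (695 zygotes".
- The fourth, 2B, is once only, 829 zygotes, with no O₂ value in the text available to us.

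Two other places use the labels. The Antioxidant Supplementation section gives repeated additions to 1A and 2A and a single addition to 1B and 2B. SAP section 10, Data Interpretation, describes 1A and 2A as the 12-hourly groups and 1B and 2B as the once-only groups. Neither ties an O₂ tension to a label. The text on control of O₂ tensions names 20% as the first setting and 5% as the second, without naming groups.

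**The concern.** The group definitions fix what is randomised and what each comparison means, and here two incompatible sets stand in one protocol. The set with the missing condition is the one attached to the random-assignment sentence. A laboratory working from that list would run two groups under the same condition and none with single supplementation at 20% O₂, so the effect of frequency could not be estimated at 20% O₂.

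The labels also carry the reported results. Under the Sample Size list, 1A versus 1B is a comparison of frequency at 20% O₂. Under the Allocation list, it is a comparison of O₂ tension with 12-hourly supplementation. The SAP's subgroup analyses by O₂ tension depend on which reading applies. So does the rest of the incubator setting, because the Embryo Culture section pairs 20% O₂ with 95% relative humidity and 5% O₂ with 25%.

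**Working it through.** **Plan's own total.** The four counts in the Sample Size list are 793 + 1286 + 695 + 829 = 3603, which matches the stated total.

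**Label by label.**

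| Label | Allocation list | Sample Size list | Zygotes | Conflict |
|---|---|---|---|---|
| 1A | 12-hourly, 5% | 12-hourly, 20% | 793 | O₂ |
| 1B | 12-hourly, 20% | once, 20% | 1286 | frequency |
| 2A | once, 5% | 12-hourly, 5% | 695 | frequency |
| 2B | once, 5% | once, O₂ not printed | 829 | none shown |

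Three of four labels conflict outright. 2B agrees on frequency. Its O₂ tension cannot be compared, and the blank may come from text extraction, so it is not counted as a conflict.

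**Distinct conditions in the Allocation list.** 12-hourly at 5%, 12-hourly at 20%, and once at 5% (printed twice). That is three; once at 20% is absent.

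**Zygotes under conflicting labels.**

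- Frequency: 1286 + 695 = 1981; 1981/3603 = 55.0%.
- O₂: 793/3603 = 22.0%.
- Either: 1981 + 793 = 2774; 2774/3603 = 77.0%.

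**What other text settles.** The Antioxidant Supplementation section and SAP section 10 both put 1A and 2A on the 12-hourly schedule and 1B and 2B on the single addition. This matches the Sample Size list and contradicts the Allocation list for 1B and 2A. Neither gives O₂ by label, so 1A stands at 5% in one list and 20% in the other.

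**How far the two readings differ.** Counts are printed only in the Sample Size list; attaching them to the Allocation labels is an assumption.

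| Quantity | Allocation labels | Sample Size labels |
|---|---|---|
| 12-hourly | 793 + 1286 = 2079 (57.7%) | 793 + 695 = 1488 (41.3%) |
| 20% O₂ | 1286 | 793 + 1286 = 2079 (excluding 2B) |
| Once only at 20% O₂ | 0 | 1286 |

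**The SAP contrast under Allocation labels.** The 1A and 2A side has 793 + 695 = 1488 zygotes, all at 5% O₂. The 1B and 2B side has 1286 + 829 = 2115, of which 1286 are at 20% and 829 at 5%. Each side holds one 12-hourly and one once-only group, so the contrast would not separate the frequencies.

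**The case against.** The best defence is that this is a documentation slip whose likely origin can be seen. In the Allocation list the number carries frequency and the letter carries O₂, except that 2B breaks the pattern. Elsewhere the letter carries frequency. A transposed labelling scheme plus one repeated line would explain the list. On frequency, three places agree and only the Allocation list dissents. The order of the O₂ settings, 20% then 5%, also parallels the order of groups 1 and 2 in the Sample Size list. The same protocol counts 1286 zygotes in a once-only group at 20% O₂, and the SAP writes the frequency beside the labels, so its frequency comparison is clear as worded. The 77.0% adds two different kinds of conflict, and the totals that attach counts to Allocation labels describe no design that the documents set out.

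Much of this stands. The frequency conflict has strong evidence on one side, the two kinds of conflict should be read separately, and the hybrid totals only measure the ambiguity. But a plausible origin is an inference. It does not supply the missing link between label and O₂ tension, and it leaves the list under the random-assignment sentence wrong for the stated aim. The conflicting entries are complete sentences, so extraction does not explain them.

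**Conclusion.** The point holds and must be fixed. Two incompatible definitions of the groups are in force, and the one under random assignment cannot deliver the comparison in the aim. The frequency conflict covers labels with 1981 zygotes (55.0%); other text bears on it, but the contradiction remains on the page. The O₂ conflict covers 793 zygotes (22.0%), and nothing else in the documents resolves it. These percentages take the printed counts as belonging to the labels beside them. They measure ambiguity in the text and are not evidence that embryos were cultured or coded wrongly. Which list is correct is not decided here.

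**What to change.** Reconcile the passages into one table giving, for each label, the supplementation frequency, the O₂ tension (including 2B) and the number of zygotes. Use it, or refer to it, in the Allocation, Sample Size and Group Allocation, and Antioxidant Supplementation sections and in the SAP. Define every comparison by its condition (frequency and O₂), not by label alone.

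Because the SAP already reports findings by label, also check the group codes in the study databases against the incubator and supplementation records, and state the result. This assumes that such records exist by group; if they do not, that should be stated.

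The cost is wording in four sections plus one retrospective check of codes, with no new data. The check is more work than the wording, and the reconciliation is needed whether or not it is done.

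### The four group sizes (793, 1286, 695, 829) contradict equal random allocation of zygotes, and no other allocation rule is documented, so the randomisation claim and the causal reading are unsupported as written

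*Protocol*

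**What the plan says.** The Allocation section of the protocol reads "Zygotes will be randomly assigned to one of four groups". The unit is therefore the zygote. No ratio, sequence generation, concealment, blocking or stratification is given there or elsewhere.

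Under Sample Size and Group Allocation the protocol states "A total of 3603 zygotes obtained from 293 patients will be included in the study" and continues "The zygotes will be divided into four groups based on the following conditions". The counts that follow are 793 (1A), 1286 (1B), 695 (2A) and 829 (2B). The largest is entered as "Group 1B: Antioxidants will be administered only at the beginning of embryo culture at 20% O₂ tension (1286 zygotes". Neither document gives the number of women per group, or says whether one woman's zygotes stay together or are split.

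The protocol defines the four groups twice, and the definitions differ. The Allocation list makes 1A and 1B the 12-hourly groups, and gives 2A and 2B identical conditions. The list with counts makes 1A and 2A the 12-hourly groups and leaves out the oxygen level of the last one: "Group 2B: Antioxidants will be administered only at the beginning of embryo culture at (829 zygotes".

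The planned comparison in both documents is an odds ratio with a chi-square test and no adjustment. The SAP's Data Interpretation section credits supplementation with better blastocyst development and draws implications for infertility treatment.

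**The concern.** An unadjusted comparison takes its causal meaning from the way the groups were formed. If zygotes had been randomised equally, the four totals would be close to one another. They are not: the largest group is 1.85 times the smallest (1286/695).

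If the groups were in fact formed by some non-random process, they may differ in more than the supplementation schedule. The protocol describes several stimulation regimens and two insemination methods, and the SAP itself concedes that other treatments may confound the result. Neither document plans an adjustment. A confounded difference would then be reported as an effect of the schedule, and nothing in the plan would reveal it.

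**Working it through.** **Inputs from the protocol.** Group counts 793, 1286, 695, 829; total 3603 zygotes; 293 women. The sum reproduces the stated total: 793 + 1286 + 695 + 829 = 3603. Mean zygotes per woman: m = 3603/293 = 12.30.

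**Assumed.** The documents do not give the spread of zygotes per woman. I use a CV of 0.3 to 0.9. Eligibility requires more than 2 fertilised oocytes and excludes women with fewer than 6 oocytes, which removes the low tail.

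**1. Zygotes as the unit (as stated), equal allocation.** Expected count E = 3603/4 = 900.75.

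X² = Σ(O − E)²/E = 12.9 + 164.8 + 47.0 + 5.7 = 230.4 on 3 df, p about 1e-49.

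The SD of one group's count is √(3603 × 0.25 × 0.75) = 26.0, so 1286 lies (1286 − 900.75)/26.0 = 14.8 SD above expectation. Splitting each woman's zygotes evenly over the groups would bring the totals even closer to equal.

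This result does not depend on which label belongs to which condition.

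**2. Whole women as the unit, simple equal allocation.** The variance of each count grows by the factor m(1 + CV²), so X² is divided by it.

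| Assumed CV | Factor | Adjusted X² (3 df) | p |
|---|---|---|---|
| 0.3 | 13.40 | 17.19 | 0.0006 |
| 0.5 | 15.37 | 14.99 | 0.0018 |
| 0.7 | 18.32 | 12.57 | 0.0057 |
| 0.9 | 22.26 | 10.35 | 0.0158 |

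Simulation with gamma-distributed cluster sizes (40,000 runs per setting) gives 0.06%, 0.2%, 0.6% and 1.4%. The p-value passes 0.05 only above a CV of about 1.18: 230.4/7.815 = 29.48, 29.48/12.30 = 2.40, √(2.40 − 1) = 1.18. If the numbers of women per group were balanced by design, an imbalance this large did not occur at CV 0.3 to 0.7 and occurred in 2 of 40,000 runs at CV 0.9.

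**3. Allocation rules that would fit.** These are illustrations; none is in the documents. The ratios were picked after seeing the counts, with the largest share given to the group of 1286.

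| Ratio | X² against it | p, zygotes | p, women (CV 0.5) |
|---|---|---|---|
| 2:3:2:2 | 21.0 | 0.0001 | 0.71 (21.0/15.37 = 1.37) |
| 1:2:1:1 | 41.2 | 6e-9 | 0.44 (41.2/15.37 = 2.68) |

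Equal allocation of batches of b women has the factor m(b + CV²). At CV 0.5 this is 39.97 for b = 3 (X² = 5.76, p = 0.12) and 52.26 for b = 4 (X² = 4.41, p = 0.22).

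**4. Margins.** These depend on the labels. With the second list, and 2B taken as 5% O₂:

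- Schedule: 793 + 695 = 1488 against 1286 + 829 = 2115. Distance from equal: (2115 − 1801.5)/√(3603/4) = 10.4 SD with zygotes as units.
- Oxygen: 793 + 1286 = 2079 against 695 + 829 = 1524. Distance from equal: (2079 − 1801.5)/30.0 = 9.2 SD.

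Under the first list's labels the schedule split would be 2079 against 1524 instead. The Antioxidant Supplementation section and the SAP use the schedule labels of the second list.

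**The case against.** The strongest reply is that unequal totals are not evidence of non-random assignment, and do not by themselves bias an odds ratio. A planned unequal ratio, arms opened at different times, exclusions after allocation, or allocation by retrieval day or incubator load could each give these counts from a genuine random list. Oxygen is set by the incubator, so a batch unit is plausible. This stands. Step 3 shows that simple ratios among women fit well, and that equal allocation of small batches would not be rejected.

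Two stronger readings therefore fail:

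- A reader might infer that the study was not randomised, or that assignment followed workload, calendar or embryologist choice. The documents mention no such mechanism, and the counts cannot establish one.
- A reader might infer that no simple design ratio could give these counts, or that only a list with a ratio near 1.1:1.9:1:1.2 would vindicate the claim. Those are realised zygote counts, not a design ratio. With women as the unit, 2:3:2:2 and 1:2:1:1 both fit.

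It is also fair to say that the result for whole women rests on a CV the documents do not report, so it is very unlikely rather than impossible.

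The reply does not remove the conflict on the page. Every explanation that fits needs an allocation rule or a later event that the protocol does not describe, and batch or whole-woman allocation contradicts the stated unit.

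**Conclusion.** The point holds in this form. Equal zygote-level allocation, the plainest reading of the protocol, is incompatible with its own counts (X² = 230.4, 3 df, p about 1e-49), and this needs no assumption beyond an equal ratio. Simple equal allocation of whole women is very unlikely: about 0.06% to 1.6% for an assumed CV of 0.3 to 0.9. Other random schemes could account for the counts, but none is documented. The randomisation claim, and the SAP's causal reading of unadjusted tests, are unsupported as written; they are not shown to be false.

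**What to change.** 1. **Replace the allocation sentence** with the rule actually used: unit (zygote, woman or batch), ratio, who or what generated the list and when, and whether a woman's zygotes could enter more than one group.
2. **Add a table** of women and zygotes per group, with any exclusions after allocation and the dates each group was open. Explain why one group has 1286.
3. **Reconcile the two group lists** in the protocol, including the missing oxygen level for 2B, so that each count is tied to one condition.
4. **If a documented random list exists, whatever its ratio,** the random-assignment wording can stay once steps 1 to 3 are done.
5. **If none exists,** remove that wording and describe the study as a non-randomised comparison. Soften the causal statements in the SAP's Data Interpretation section. Replace the unadjusted chi-square as the main estimate with one that clusters on the woman and adjusts for recorded woman-level factors (such as age, insemination method and stimulation regimen) and calendar month.

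**Cost.** Steps 1 to 3 are wording and one table. Step 5 weakens the design label and the causal claim and needs a new main analysis. It assumes that the adjustment factors can be retrieved from clinic records, which the documents do not confirm.

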Statistical analysis plan:

Impact of Repeated Antioxidant Supplementation of Embryo Culture Media on Blastocyst Utilization and Expansion Rate Under Two Different O₂ Concentrations

October 31st, 2021

Research Questions:

- What is the effect of antioxidant supplementation and O2 tension on blastocyst utilization rate and blastocyst expansion rate in infertile women?
- Are there any significant differences in the outcomes between the different antioxidant supplementation protocols and O2 tensions?

Statistical Tests:**Sample Size:**

The total number of blastocysts analyzed was 1797, obtained from 3603 zygotes and 4924 inseminated oocytes. The study included 293 infertile women with a mean age of 32.2 ± 3.3 years.

Data Handling:

For statistical analysis, the data collected consisted of the continuous variable of age, which was expressed as the mean \pm standard deviation in each study group. In addition, the frequency and percentage of usable and expanded blastocysts were recorded as categorical variables.

Comparisons between treatments were performed by calculating the odds ratio and the chi-square test. A significance level of $p < 0.05$ was established to determine the existence of statistically significant differences between groups.

Confounding Variables:

Other treatments or medications: Although there is no explicit mention of other treatments or medications received by the participants in addition to antioxidant supplementation, it is essential to acknowledge that there may be confounding variables present. It is possible that other interventions or medications used in the management of infertility could interact with antioxidant supplementation and potentially influence the study outcomes.

Sensitivity analysis:

The odds ratio analysis with a confidence interval of 95%

9. Statistical Software:

R Core Team was employed for statistical analysis.

10. Data Interpretation:

The results were interpreted by analyzing and comparing the blastocyst utilization rates, blastocyst expansion rates, and cumulative blastocyst utilization and expansion rates across the four study

groups. Statistical analyses, such as odds ratios (OR) and chi-square tests, were used to determine the significance of the differences observed. The level of significance was set at $p < 0.05$.

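### The only rate formula given divides expanded blastocysts by blastocysts, although zygotes are allocated; followed as written, the expansion comparison conditions on a post-allocation event

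*Protocol*

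**What the plan says.** **Allocation and start of treatment.** The Protocol, under Allocation, says "Zygotes will be randomly assigned to one of four groups". Under Embryo Culture it limits the study unit: "Only 2 pronuclei (PN) zygotes will be considered for the study". Under Antioxidant Supplementation, the first dose in groups 1A and 2A "will be added at the beginning of the culture (in the zygote stage"), so the groups begin to differ before any blastocyst exists. Under Sample Size and Group Allocation: "A total of 3603 zygotes obtained from 293 patients will be included in the study".

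**The rate.** The Protocol, Data Collection (Variables to be Measured), gives the only formula for a rate in either document: "The blastocyst expansion rate will be assessed by calculating the proportion of blastocysts that reach the expanded stage".

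**Outcomes and tests.** Outcome Measures lists usable and expanded blastocysts on day 5, on day 6 and cumulatively, with no denominator. Statistical Methods adds none: "Comparisons between usable and expanded blastocysts from each treatment were performed by calculating the odds ratio and chi-square test". The SAP, Data Interpretation, is equally silent: "The results were interpreted by analyzing and comparing the blastocyst utilization rates, blastocyst expansion rates, and cumulative blastocyst utilization and expansion rates".

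**Number analysed.** The SAP, Sample Size, says "The total number of blastocysts analyzed was 1797, obtained from 3603 zygotes and 4924 inseminated oocytes".

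**The concern.** Reaching the blastocyst stage happens after allocation and after treatment has begun. A comparison made only among embryos that got there can differ between groups because treatment changed expansion, because it changed which embryos became blastocysts, or both. The protocol's own Introduction says that antioxidants have been shown to help embryos reach the blastocyst stage, so on the sponsor's rationale an effect on blastocyst formation is plausible. That statement is about antioxidants in general; it does not address repeated against single addition.

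The stake is how the main conclusion reads. The SAP, Data Interpretation, reports higher expansion rates with 12-hourly addition and draws practical implications, but does not say per what. Blastocyst formation by group is not a listed outcome. A reader therefore cannot tell whether more of the allocated zygotes became expanded blastocysts, or only a larger share of those that became blastocysts.

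**Working it through.** **1. The plan's own total.** The group sizes in Protocol, Sample Size and Group Allocation, are 793 + 1286 + 695 + 829 = 3603, which matches the stated total.

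**2. Share retained under the literal rule.** 1797 / 3603 = 49.9%, and 3603 - 1797 = 1806 (50.1%) are left out. This takes the 1797 to be all blastocysts formed and to be the expansion denominator; the SAP states neither. The 1797 is not split by day or by group, so the figure can apply only to the cumulative outcome.

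**3. How the two denominators relate.** For each group, expanded per zygote = (blastocysts per zygote) x (expanded per blastocyst). Hence

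per-zygote risk ratio = per-blastocyst risk ratio x ratio of blastocyst formation.

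The last factor is not given anywhere. If it is above 1, the per-blastocyst ratio understates the per-zygote ratio; if below 1, it overstates it; if equal to 1, the two risk ratios agree.

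**4. Illustration with assumed rates.** Only the zygote counts and the 1797 total come from the documents. Pooling over oxygen, as labelled in the list that carries counts, 12-hourly is 793 + 695 = 1488 and once only is 1286 + 829 = 2115. For an assumed 12-hourly formation rate b1, the once-only rate that keeps the total is b2 = (1797 - 1488 x b1) / 2115.

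(a) Assume 30% expanded per zygote in both arms, so the per-zygote odds ratio (OR) is 1.00. Expanded per blastocyst is then 0.30 / b.

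| Formation, 12-hourly v once | Expanded per blastocyst | Per-blastocyst OR |
|---|---|---|
| 45.0% v 53.3% | 66.7% v 56.3% | 1.55 |
| 48.0% v 51.2% | 62.5% v 58.6% | 1.18 |
| 49.9% v 49.9% | 60.1% v 60.1% | 1.00 |
| 52.0% v 48.4% | 57.7% v 62.0% | 0.84 |
| 55.0% v 46.3% | 54.5% v 64.8% | 0.65 |

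With 25% to 35% expanded per zygote, the first row ranges from 1.42 to 1.83 and the last from 0.71 to 0.56.

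(b) In the direction the SAP reports, assume 65% v 60% expanded per blastocyst: risk ratio 0.65 / 0.60 = 1.08, OR 1.24.

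| Formation, 12-hourly v once | Expanded per zygote | Per-zygote risk ratio |
|---|---|---|
| 48.0% v 51.2% | 31.2% v 30.7% | 1.02 |
| 49.9% v 49.9% | 32.4% v 29.9% | 1.08 |
| 52.0% v 48.4% | 33.8% v 29.0% | 1.16 |

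With equal formation the risk ratio is unchanged, while the OR moves from 1.24 per blastocyst to 1.12 per zygote. The direction is the same.

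These are point estimates. They show what the denominator can do; they do not estimate what it did.

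**The case against.** The strongest reply is that one loosely worded line under Variables to be Measured does not fix the denominator of the tests. Group sizes are given in zygotes, the stated aim speaks of rates in human embryos, and neither analysis section names a denominator, so a per-zygote analysis is not excluded. This stands. A reader might infer that half the allocated zygotes were in fact dropped from the tests; the documents do not show that. But if a per-zygote rate was meant, the one formula contradicts it and needs correcting; if not, the comparison is conditioned. Either way the text has to change.

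A reader might also infer that the reported advantage of 12-hourly addition is an artefact. The documents do not support this either. Inflation requires that 12-hourly addition lowered blastocyst formation, and nothing suggests that it did. What the Introduction says about antioxidants in general would point towards understatement, though it does not settle the contrast between schedules.

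Nor is it shown that the usable outcomes are conditioned on blastocyst formation. Their denominator is simply undefined.

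Finally, expanded per blastocyst is a coherent measure of blastocyst quality, and the Introduction treats expansion as a quality grade. That is a good reason to keep it, but not to rest the between-group conclusion on it.

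**Conclusion.** The point holds as a defect in a stated rule. Followed as written, the protocol's expansion rate conditions on an event after allocation, and no other section supplies a per-zygote comparison. Whether the tests were actually run that way is not stated.

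The 1806 of 3603 (50.1%) holds for the cumulative expansion outcome only, under the two assumptions about the 1797 set out in the working. The actual size and direction of any distortion cannot be computed from the documents. The illustrations show that moderate differences in blastocyst formation could create, shrink or enlarge an apparent difference; they are not evidence that this occurred.

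The change should be made because it affects how a core outcome is read and costs little.

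**What to change.** In the protocol and SAP:

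- Define the between-group expansion comparisons (day 5, day 6 and cumulative) as expanded blastocysts over all 2PN zygotes allocated to the group.
- State the same denominator for the usable outcomes.
- Report blastocyst formation per zygote by group.
- Keep expanded per blastocyst as a secondary quality measure, not as the basis for the between-group conclusion.
- Label the re-analysis post hoc, since the SAP already reports results.

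The two group lists in the protocol (under Allocation, and under Sample Size and Group Allocation) describe the groups differently, and the second gives no oxygen level for group 2B. This is a separate issue, but the lists must be reconciled before counts are tied to groups.

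The cost is a sentence on denominators in each document, one added table row, and a small re-analysis of counts already held; no new data are needed. The downside is that the expansion percentages will be lower than on a per-blastocyst basis.
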